5 STATISTICAL METHODS

All descriptive statistics for continuous variables will be reported using mean, standard deviation (SD), median, minimum and maximum. Categorical variables will be summarized as number (percentage) of subjects.

5.1 Study Endpoints

5.1.1 Primary Endpoint

The primary endpoint is defined as follows.

The seizure free rate in the 26-week Maintenance Period for subjects with POS

The number (percentage) of subjects with POS who achieved seizure-free during the 26-week Maintenance Period of 4 mg and regardless of perampanel dose will be calculated. For subjects who increase the perampanel dose from 4 mg to 8 mg, the seizure-free rate of

the 26-week Maintenance Period of 8 mg will be evaluated to calculate the number (percentage) of subjects who achieved seizure-free regardless of perampanel dose.

5.1.2 Secondary Endpoints

The secondary endpoints are defined as follows.

- The seizure free rate in the 52-week treatment (ie, 26-week Maintenance Period plus 26-week Extension Phase) for subjects with POS
- Time to first seizure onset and time to withdrawal from the study from the first date of the Maintenance Period
- The safety and tolerability of perampanel

5.1.3 Exploratory Endpoints

The exploratory endpoints are defined as follows.

- The seizure free rate in the 26-week Maintenance Period for subjects with POS by types of partial seizure
- The percent change in seizure frequency of POS per 12 weeks in the Maintenance Period and Extension Phase relative to the Pretreatment Phase
- The pharmacokinetics of perampanel as monotherapy
- The effect of perampanel on subjects' quality of life with EQ-5D-5L measurements

5.2 Study Subjects

5.2.1 Definitions of Analysis Sets

Safety Analysis Set

The Safety Analysis Set is the group of subjects who sign informed consent, receive at least 1 dose of study drug and have at least 1 postdose safety assessment.

Intent-to-Treat (ITT) Analysis Set

The ITT Analysis Set is the group of subjects who sign informed consent, receive at least 1 dose of study drug and have at least 1 postdose primary efficacy measurement.

Modified Intent-to-Treat (mITT) Analysis Set

The mITT Analysis Set is the subset of the ITT Analysis Set who enter the 4 mg Maintenance Period and have at least 1 postdose primary efficacy measurement in the 26-week Maintenance Period.

The number of subjects enrolled, the number (percentage) of subjects included in each analysis set will be presented. Subject data listings will be provided.

5.2.2 Subject Disposition

For the summary table of screening subjects, the number (percentage) of subjects who were enrolled (ie, subjects who signed informed consent), entered the Treatment Phase after screening, failed screening, and the primary reason for screen failures will be presented.

For the summary of the subject disposition, the following items will be presented;

- the number (percentage) of subjects who were treated/not treated
- the number (percentage) of subjects who completed/discontinued the 4 mg Treatment Phase and the primary reason and other reason for the discontinuation
- the number (percentage) of subjects who entered/completed/ongoing/discontinued the 8 mg Treatment Phase and the primary reason and other reason for the discontinuation
- the number (percentage) of subjects who completed/ongoing/discontinued the Treatment Phase and the primary reason and other reason for the discontinuation
- the number (percentage) of subjects who entered/not entered the Extension Phase
- the number (percentage) of subjects who completed/ongoing/discontinued the Extension Phase and the primary reason and other reason for the discontinuation (the percentage will be based on the total subjects who entered the Extension Phase)

Subject data listings will be provided.

5.2.3 Protocol Deviations

Major protocol deviation criteria will be established and subjects with major protocol deviations will be identified and documented before the database lock.

5.2.4 Demographic and Other Baseline Characteristics

This summary table will be generated on the ITT Analysis Set and Safety Analysis Set. (This will be summarized as “ITT / Safety Analysis Set” if the ITT Analysis Set and the Safety Analysis Set are the same.) This summary table will also be generated on the mITT Analysis Set. And this summary table will be performed by country (Japan/ Korea).

Continuous demographic and baseline variables include

- Age
- Height
- Weight
- BMI

Categorical demographic and baseline variables include

- Age group (< 18 years, 18 - < 65 years, 65years ≤)
- Sex
- Race
- Ethnicity
- Country

Epilepsy specific history and characteristics at study entry will also be summarized by:

- History of seizures (newly diagnosed epilepsy, recurrent epilepsy)

- Time since latest diagnosis of epilepsy (months)
- Etiology
- Epileptic syndrome
- Suspected localization of the epileptogenic region
- Seizure type

Subject data listings for demographic and other baseline characteristics will be provided.

MEDICAL HISTORY

A subject data listing of medical history and current medical condition will be provided.

5.2.5 Prior and Concomitant Therapy

All investigator terms for medications recorded in the CRF will be coded to an 11-digit code using the World Health Organization Drug Dictionary (WHO DD) drug codes.

Prior medications will be defined as medications that stopped before the first dose of study drug. Concomitant medications will be defined as medications that (1) started before the first dose of study drug and were continuing at the time of the first dose of study drug, or (2) started on or after the date of the first dose of study drug up to the completion or discontinuation of the subject after the subject's last dose. Post-treatment medications will be defined as medications taken on or after the date of study discontinuation.

This summary table will be generated on the ITT Analysis Set and Safety Analysis Set. (This will be summarized as "ITT / Safety Analysis Set" if the ITT Analysis Set and the Safety Analysis Set are the same.)

The number (percentage) of subjects who took prior anti-epileptic medications will be summarized by Anatomical Therapeutic Chemical (ATC) class, and WHO DD preferred term. This analysis will also be performed by both history of seizures (newly diagnosed epilepsy/recurrent epilepsy) and rescue (yes/no).

The number (percentage) of subjects who took prior (except for anti-epileptic medications) and concomitant medications will be summarized by Anatomical Therapeutic Chemical (ATC) class, and WHO DD preferred term.

The concomitant medications will be summarized for the Treatment Phase and the entire study period (ie, the Treatment Phase or the Extension Phase).

All medications will be presented in subject data listings.

5.2.6 Treatment Compliance

Treatment compliance calculated as follows will be summarized using descriptive statistics for the 26-week Maintenance Period of 4 mg and the 26-week Maintenance Period of the last evaluated dose (ie, 4 or 8mg) on the mITT Analysis Set.

$$\frac{\text{Total days of study drug prescribed} - \text{Days of incompliance}}{\text{Total days of study drug prescribed}} \times 100$$

The number (percentage) of subjects in the categories <80%, >= 80% to <= 100%, >100% to <= 120%, and > 120% will also be summarized.

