#### 9.4.8 Treatment Compliance

Records of treatment compliance for each subject will be kept during the study. Clinical research associates (CRAs) will review treatment compliance during site visits and at the completion of the study.

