#### 9.5.4.3 Reporting of Events Associated with Special Situations

##### 9.5.4.3.1 REPORTING OF ADVERSE EVENTS ASSOCIATED WITH STUDY DRUG OVERDOSE, MISUSE, ABUSE, OR MEDICATION ERROR

Adverse events associated with study drug overdose, misuse, abuse, and medication error refer to AEs associated with uses of the study drug outside of that specified by the protocol. Overdose, misuse, abuse, and medication error are defined as follows:

|                  |  |
|------------------|--|
| Overdose         | Accidental or intentional use of the study drug in an amount higher than the protocol-defined dose   |
| Misuse           | Intentional and inappropriate use of study drug not in accordance with the protocol  |
| Abuse            | Sporadic or persistent intentional excessive use of study drug accompanied by harmful physical or psychological effects  |
| Medication error | Any unintentional event that causes or leads to inappropriate study drug use or subject harm while the study drug is in the control of site personnel or the subject |

All AEs associated with overdose, misuse, abuse, or medication error should be captured on the Adverse Event CRF and also reported using the procedures detailed in Reporting of Serious Adverse Events (Section 9.5.4.1) even if the AEs do not meet serious criteria. Abuse

is always to be captured as an AE. If the AE associated with an overdose, misuse, abuse, or medication error does not meet serious criteria, it must still be reported using the SAE form and in an expedited manner but should be noted as nonserious on the SAE form and the Adverse Event CRF.

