5.5 Pharmacokinetic, Pharmacodynamic, Pharmacogenomic, and Other Biomarker Analyses

5.5.1 Pharmacokinetic Analyses

The Safety Analysis Set will be used for individual perampanel plasma concentration listings and summaries of perampanel plasma concentrations. Plasma perampanel concentration data at Early transition visit or Early discontinuation visit will not be included in tables and figures for pharmacokinetic analysis. The plasma perampanel concentration data will be excluded from the plasma concentration analysis if the treatment compliance during site visits at Visit 4, 5, 7, 4a, 5a, or 7a where PK blood sampling will be conducted is inadequate for PK evaluation including following cases but not limited to:

- The dose amount is not constant during the last 3 doses of perampanel before PK blood sampling at Visit 4, 5, 7, 4a, 5a, or 7a.
- The perampanel is not administered on consecutive 3 days just before PK blood sampling at Visit 4, 5, 7, 4a, 5a, or 7a.
- Treatment compliance rate during site visits before PK blood sampling at Visit 4, 5, 7, 4a, 5a, or 7a is <80%.

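### The compliance formula in SAP 5.2.6 cannot exceed 100%, so its two over-use categories will always be empty

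*SAP*

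**What the plan says.** SAP 5.2.6 adds a compliance summary that the protocol does not contain: "Treatment compliance calculated as follows will be summarized using descriptive statistics for the 26-week Maintenance Period of 4 mg", and likewise for the Maintenance Period of the last evaluated dose, both on the mITT set. The denominator is "Total days of study drug prescribed". The numerator is that same quantity less "Days of incompliance", and the result is multiplied by 100. The categories follow directly: below 80%, then 80% to 100%, and then ">100% to <= 120%, and > 120% will also be summarized".

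Neither document defines an incompliant day. Protocol 9.4.8 says only that "Records of treatment compliance for each subject will be kept during the study" and that monitors will review compliance. SAP section 9 places derivation rules in separate documents, which are not available here.

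A compliance rate appears once more, in SAP 5.5.1, among the reasons for excluding a plasma concentration: "Treatment compliance rate during site visits before PK blood sampling at Visit 4, 5, 7, 4a, 5a, or 7a is <80" percent. That section does not refer back to 5.2.6 and gives no formula of its own.

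**The concern.** The formula and the table it feeds do not fit each other. Two of the four categories describe subjects who took more than was prescribed, but subtracting a number of days from the days prescribed cannot give more than 100%. Those rows will be zero by construction, and a reader of the study report would take them as evidence that nobody over-used the drug.

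Over-use is something the plan recognises. Protocol 9.5.4.3.1 defines overdose as "Accidental or intentional use of the study drug in an amount higher than the protocol-defined dose". The exposure summary in SAP 5.6.1 would not show it, because dose there means planned rather than actual dose. The reporting in Protocol 9.5.4.3.1 concerns adverse events associated with overdose. Over-use that produced no adverse event, and was not abuse, would therefore appear in neither place.

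Because an incompliant day is undefined, it is also unclear what the formula does with a day on which extra tablets were taken.

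**Working it through.** The documents state no result for this formula, so there is no figure to reproduce. The check is on its range, followed by an example.

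**Inputs**
- T = days of study drug prescribed. For the 4 mg Maintenance Period, Protocol Table 1 gives Days 43 to 224, so T = 224 − 43 + 1 = 182.
- D = days of incompliance, a count with D ≥ 0 on its ordinary meaning (SAP 5.2.6).
- Category limits of 80%, 100% and 120% (SAP 5.2.6).
- k = days on which a subject takes double the prescribed dose. This is an assumption for illustration. The documents give no such figure.

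**Range of the formula**

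C = (T − D)/T × 100 = 100 × (1 − D/T). With D ≥ 0, C ≤ 100 for every T. Enumerating T from 1 to 400 and D from 0 to T gives a maximum of exactly 100.0%. For T = 182 there are 183 possible values, running from 0% to 100%, and none exceeds 100%.

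**What happens to over-use (T = 182)**

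Three calculations are compared:
- Reading A, where an over-use day counts as incompliant: (182 − k)/182 × 100.
- Reading B, where only missed days count: (182 − 0)/182 × 100.
- Amount-based ratio, doses taken over doses prescribed: (182 + k)/182 × 100.

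| k | Reading A | Reading B | Amount-based |
|---|---|---|---|
| 10 | 94.5% | 100.0% | 105.5% |
| 36 | 80.2% | 100.0% | 119.8% |
| 37 | 79.7% | 100.0% | 120.3% |

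For k = 37 in full: A = 145/182 = 79.7%, the same score as 37 missed days; B = 182/182 = 100.0%; amount-based = 219/182 = 120.3%. At two 2 mg tablets a day (Protocol Table 1), the last figure is (364 + 74)/364 = 438/364 = 120.3%.

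Under A the subject moves from the second category to the lowest once k reaches 37. Under B the subject stays in the second category. Neither reading can place the subject in an over-use category, while the amount-based ratio reaches both of them.

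**Whether the SAP 5.5.1 rate is the same figure**

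SAP 5.2.6 covers the 26-week Maintenance Periods on the mITT set. SAP 5.5.1 uses a rate tied to site visits before sampling, on the Safety Analysis Set. Its visits include 4 and 4a, which fall at the end of the two Titration Periods (SAP 5.5.1.1; Protocol Tables 3 and 4). A maintenance-period figure cannot be the one applied at those visits. The same formula may be intended over a different interval, but the SAP does not say so.

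**The case against.** The separate programming documents may define an incompliant day. They could settle the choice between readings A and B. They could not fill the upper categories without negative days or a different formula, and either would depart from what SAP 5.2.6 states. The mismatch stands.

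A reader might infer that over-use days are certainly subtracted like missed doses. The documents do not say so. That is reading A, and reading B is equally open. Even under A, modest over-use stays in the second category: ten double-dose days score 94.5%.

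A reader might also infer that the 5.2.6 figure itself decides which PK samples are dropped. The interval and the analysis set differ, so this is not supported. SAP 5.5.1 also excludes samples when the last three doses were not constant, and its list is open-ended, so recent over-use can be caught in other ways.

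Two objections to an amount-based formula have force. First, the documents place dispensing and return counts in site logs and ledgers (Protocol 9.4.9 and 11.8) and compliance on the CRF (Protocol 11.5). Nothing shows tablet counts in the analysis database. Second, a ratio above 100% passes a rule that excludes only rates below 80%, so changing the formula alone could retain an over-user's samples that reading A would have excluded.

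Finally, the summary is descriptive and SAP section 7 lists it among the minor changes. Adverse events associated with overdose have their own reporting route, and abuse is always recorded as an adverse event. This keeps the point at the lowest severity, but it does not make the table correct.

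**Conclusion.** The point holds in a limited form. The SAP 5.2.6 formula has a ceiling of 100%, so two of its four categories are unreachable and would report no over-use regardless of the facts. This rests only on days of incompliance being a non-negative count. How over-use is scored is undetermined: in the 37-day example it is 79.7% or 100.0%, against 120.3% by amount taken. That example assumes exact double dosing and a full 182-day period.

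The consequences are a misleading descriptive table and, if the same formula is reused in SAP 5.5.1, possibly the exclusion or retention of some PK samples. No efficacy endpoint, efficacy analysis set or decision rule uses compliance, so the primary result is untouched.

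**What to change.** Settle this in the SAP before database lock. The protocol gives no compliance formula, so none has to be amended there.

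1. **If dispensed and returned tablet counts are in the database:** define compliance as tablets dispensed minus tablets returned, divided by tablets prescribed, times 100, and keep the four categories. Unused medication is returned at Visits 3 to 9 and 2a to 9a (Protocol Tables 3 and 4) and reconciled at sites. The cost is that a lost or unreturned tablet counts as taken, which can create apparent over-use.
2. **If the counts are not available:** keep the day-based formula, define an incompliant day as a missed-dose day, report days of over-use separately where recorded, and delete the two categories above 100%. The cost is that over-use is shown only as far as it was recorded.
3. **In SAP 5.5.1:** state which formula and which interval the <80% exclusion uses, and say that over-use is judged separately, because a ratio above 100% would pass that rule.

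The second option needs only text and table-shell edits, apart from any listing of recorded over-use. The first also needs confirmation that the counts were collected and a reprogrammed derivation.

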5.3 Data Analysis General Considerations

5.3.1 Pooling of Centers

Subjects from all centers will be pooled for all analyses.

5.3.2 Adjustments for Covariates

No adjustment for covariates will be performed.

5.3.3 Multiple Comparisons/Multiplicity

No statistical comparison is planned in this study.

5.3.4 Examination of Subgroups

Primary efficacy analysis, the key secondary efficacy analysis and analysis of TEAEs by SOC and PT will be performed by the following subgroups: history of seizures (Newly diagnosed epilepsy/Recurrent epilepsy), age group (<18, ≥18 to <65, ≥65), country (Japan/Korea) and sex (Male/Female).

5.3.5 Handling of Missing Data, Dropouts, and Outliers

The details of handling of missing data will be described in [section 8](#).

5.3.6 Other Considerations

Not applicable.

5.4 Efficacy Analyses

All efficacy analyses will be summarized with available data in the clinical database at the data cutoff. The efficacy analysis will be performed based on the mITT Analysis Set, unless otherwise indicated.

5.4.1 Primary Efficacy Analyses

The number (percentage) of subjects with POS who achieved seizure-free during the 26-week Maintenance Period of 4 mg and the exact corresponding 95% confidence interval (CI) will be calculated on the mITT Analysis Set. The primary interest of this study will be to confirm that the exact 95% lower CI is above the pre-specified threshold (ie, 40%). If subjects experience no seizures during the 4 mg Maintenance Period, those will be regarded as seizure-free in this analysis. Otherwise, subjects will be regarded as non-seizure-free.

The definition of seizure-free status will be detailed in the [section 8](#).

SENSITIVITY ANALYSIS

Sensitivity analyses for the primary efficacy analysis will be performed on the ITT Analysis Set.

5.4.2 Secondary Efficacy Analyses

The number (percentage) of subjects with POS who achieved seizure-free during the 26-week Maintenance Period regardless of perampanel dose and the exact corresponding 95% CI will be calculated. To examine if the 95% lower CI exceeds the threshold (ie, 40%) is the key secondary efficacy analysis. The 26-week Maintenance Period mentioned here is the Maintenance Period of the last evaluated dose (ie, 4 or 8mg).

The number (percentage) of subjects with POS who achieved seizure-free during the 52-week treatment of 4 mg (ie, 26-week Maintenance Period of 4 mg and 26-week Extension Phase) and the corresponding 95% CI will be calculated.

The number (percentage) of subjects with POS who achieved seizure-free during the 52-week treatment (ie, 26-week Maintenance Period and 26-week Extension Phase) and the corresponding 95% CI will be calculated. The 26-week Maintenance Period mentioned here is the Maintenance Period of the last evaluated dose.

Median, Q1 and Q3 time to first seizure onset will be estimated by Kaplan-Meier method. The cumulative probability of the event (ie, seizure occurrence) at every 26 weeks will also be calculated. Corresponding 2-sided 95% CIs will also be presented. Kaplan-Meier estimates of the time to event will be plotted over time. The Follow-up Phase will not be included in this analysis. The above analysis will be summarized for the entire study period of 4 mg and the entire study period of the last evaluated dose, respectively.

Time to first seizure onset will be defined as the period from the first dose of study drug in the Maintenance Period of the last evaluated dose to the first seizure onset. The censoring rule for the analysis of time to first seizure onset will be provide in the [section 8](#).

Median, Q1 and Q3 time to withdraw from the study will be estimated by Kaplan-Meier method. The cumulative probability of the event (ie, withdraw from the study) at every 26 weeks will also be calculated. Corresponding 2-sided 95% CIs will also be presented. Kaplan-Meier estimates of the time to event will be plotted over time. The Follow-up Phase will not be the period to be analyzed. The above analysis will be summarized for the entire study period of 4 mg and the entire study period of the last evaluated dose, respectively.

Time to withdraw from the study will be defined as the period from the first dose of study drug in the Maintenance Period of the last evaluated dose to the date of study withdrawal. The censoring rule for the analysis of time to first seizure onset will be provide in the [section 8](#).

5.4.3 Exploratory Efficacy Analyses

The number (percentage) of subjects with POS who achieved seizure-free during the entire study period and the corresponding 95% confidence interval (CI) will be calculated. The above analysis will also be summarized for the period between the Maintenance Period of the last evaluated dose and the date of data cutoff or the date of study discontinuation, whichever comes first.

The number (percentage) of subjects with POS who achieved seizure-free during the 26-week Maintenance Period of 4 mg and the 26-week Maintenance Period of the last

evaluated dose, and each corresponding 95% confidence interval (CI) will be calculated by types of partial seizure (ie, complex partial seizures, complex partial with secondarily generalized seizure, total of the 2 type).

The number (percentage) of subjects with POS who achieved seizure-free during the 52-week treatment of 4 mg (ie, 26-week Maintenance Period of 4 mg and 26-week Extension Phase) and the corresponding 95% CI will be calculated in subjects who had been scheduled to complete 52-week treatment and mITT analysis set. The above analysis will be performed by country, and will also be performed for subjects who completed 26-week maintenance period of 4 mg and did not enter extension phase excluded.

The number (percentage) of subjects with POS who achieved seizure-free during the 52-week treatment (ie, 26-week Maintenance Period and 26-week Extension Phase) and the corresponding 95% CI will be calculated in subjects who had been scheduled to complete 52-Week treatment and mITT analysis set. The 26-week Maintenance Period mentioned here is the Maintenance Period of the last evaluated dose. The above analysis will be performed by country, and will also be performed for subjects who completed 26-week maintenance period of 4 mg and did not enter extension phase excluded.

Median, Q1 and Q3 time to first seizure onset will be estimated by Kaplan-Meier method by country. The cumulative probability of the event (ie, seizure occurrence) at every 26 weeks will be calculated by country. Corresponding 2-sided 95% CIs will also be presented by country. The Follow-up Phase will not be included in this analysis. The above analysis will be summarized for the entire study period of 4 mg and the entire study period of the last evaluated dose, respectively.

Median, Q1 and Q3 time to withdraw from the study will be estimated by Kaplan-Meier method by country. The cumulative probability of the event (ie, withdraw from the study) at every 26 weeks will also be calculated by country. Corresponding 2-sided 95% CIs will also be presented by country. The Follow-up Phase will not be the period to be analyzed. The above analysis will be summarized for the entire study period of 4 mg and the entire study period of the last evaluated dose, respectively.

The number (percentage) of subjects with POS who achieved seizure-free during the 26-week Maintenance Period of 4 mg and the 26-week Maintenance Period of the last evaluated dose, and each corresponding 95% CI will be calculated by Medical History of Simple Partial Seizure Type.

The percent change in seizure frequency of POS per 12 weeks in the Maintenance Period of the last evaluated dose and Extension Phase relative to the baseline will be summarized, respectively. The derivation of seizure frequency will be defined in the [section 8](#).

The change in EQ-5D-5L measurements from baseline to each postbaseline (ie, the Treatment Phase and the Extension Phase) visit, end of treatment phase (the 26-week Maintenance Period of the last evaluated dose) and end of treatment (the entire study of the last evaluated dose) will be summarized.

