#### 9.1.2.1 4 mg Titration and Maintenance Period

In the 4 mg Titration Period (6 weeks), subjects will initiate 2 mg QD of perampanel for 2 weeks and then will be up-titrated to 4 mg QD and will continue for 4 weeks. If subjects have no safety issues at the end of the Titration Period, they will start the 4 mg Maintenance Period for 26 weeks.

If subjects experience seizures during the 4 mg Maintenance Period, the investigator will end the 4 mg Maintenance Period and judge the transition to the 8 mg Titration Period based on the subject's tolerability and safety. If subjects could not continue 4 mg dosing due to intolerable adverse event during the 4 mg Maintenance Period, they will discontinue the study.

During the 2 weeks of Weeks 3 and 4 in the 4 mg Titration Period, if subjects are suspected to have tolerability issues for 4 mg dosing due to occurrence of adverse events, 2 mg QD can be administered in accordance with the investigators' discretion. In that case, subjects will visit the investigational site via unscheduled visit within 4 weeks after starting study treatment and will be up-titrated to 4 mg QD (for subjects who has continued 4 mg QD, occurrence of AEs will be confirmed via telephone). All subjects will continue 4 mg QD during the 2 weeks of Weeks 5 and 6. If subjects could not continue 4 mg QD due to intolerable adverse event, they will discontinue the study.

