#### 9.1.3 Extension Phase

When subjects complete the Treatment Phase and agree to continue receiving the perampanel monotherapy, they could enter the Extension Phase. Subjects who complete the 26-week Maintenance Period will continue the last dose of the Maintenance Period. Subjects who end the Treatment Phase due to insufficient efficacy or safety issue before the completion of the 26-week Maintenance Period will adjust their appropriate dose (within 4 – 8 mg of perampanel) and continue the Extension Phase. Subjects will be allowed to adjust within 2 – 8 mg of perampanel with investigators' consideration for their condition of the seizures and/or tolerability. During whole study period, the maximum dose of perampanel is 8 mg QD. The dose will be increased at intervals of 1 week or more in increments of 2 mg.

If subjects need to take other antiepileptic drugs (AEDs) or withdraw perampanel because of insufficient efficacy or tolerability issue of perampanel by the investigator's judgement, they will discontinue the study.

Once perampanel monotherapy is approved in each country, an End of Study Visit should be conducted promptly, and the subject would have to switch to the commercial product. If a subject does not switch to the commercial product promptly, an End of Study Visit and a Follow-up Visit should be conducted for the subject.

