8.2 Efficacy Data Handling

Definition of Seizure-Free status

The definition of seizure-free for perampanel 4 mg will be as follows;

The subjects who completed the 4 mg Treatment Phase with no seizures will be treated as Seizure-Free status. The subjects who had any seizures will also be treated as Seizure-Free status only if the seizure(s) appeared after the Day 183 (ie, the target visit date of the 26th week of 4 mg Maintenance Period). Day 1 is the date of first dose of study drug in the 4 mg Maintenance Period. Otherwise, subjects will be regarded as non-Seizure-Free for the evaluation of perampanel 4 mg.

The definition of seizure-free for perampanel total (regardless of doses) will be as follows;

The subjects who completed the Treatment Phase of the last evaluated dose (ie, 4 or 8 mg) with no seizures will be treated as Seizure-Free status. The subjects who had any seizures will also be treated as Seizure-Free status if the seizure(s) appeared after the Day 183 (ie, the target visit date of the 26th week of Maintenance Period for the last evaluated dose). Day 1 here is the date of first dose of study drug in the Maintenance Period of the last evaluated dose. If subjects who were titrated up to 8 mg but down-titrated to 6 mg due to tolerability issue continued the study and completed the Maintenance Period with no seizure, those will also be treated as Seizure-Free status. Otherwise, subjects will be regarded as non-seizure-free.

Handling of seizure frequency

- **Baseline**

Baseline seizure frequency will be composed of the record based on the interview at visit 1 and the dispensed diary. Baseline seizure frequency will be calculated as the number of seizures per 12 weeks (see below).

$\frac{\text{Sum of seizures during baseline}}{\text{the number of days (84 days plus the study days during the Pretreatment Phase)}} \times 84$

Study days during the Pretreatment Phase will be the period between the date of obtaining informed consent and the date of first study drug dosing (ie, the date of study drug dispensing for visit 2).

- **Post-Baseline (Maintenance Period and Extension Phase)**

Post-baseline seizure frequency will be composed of the dispensed diary. Post-baseline seizure frequency will be calculated as the number of seizures per 12 weeks (see below). The Follow-up Phase will not be included in this analysis.

$\frac{\text{Sum of seizures during post-baseline}}{\text{the number of study days during post-baseline}} \times 84$

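### The supplementary 52-week analysis at the last evaluated dose excludes Extension decliners who completed 4 mg Maintenance, but not those who completed 8 mg

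*SAP*

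**What the plan says.** SAP 5.4.3 contains two paragraphs on 52-week seizure freedom, meaning 26 weeks of Maintenance plus 26 weeks of Extension. The first concerns 4 mg. The second concerns the last evaluated dose and states: "The 26-week Maintenance Period mentioned here is the Maintenance Period of the last evaluated dose". SAP 5.4.2 gives that dose as 4 or 8 mg.

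Both paragraphs use the same two populations, worded in the 4 mg paragraph as "in subjects who had been scheduled to complete 52-week treatment and mITT analysis set". Both end with the same supplementary version, which "will also be performed for subjects who completed 26-week maintenance period of 4 mg and did not enter extension phase excluded".

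Three other provisions matter:

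- Protocol 9.1.3 makes Extension entry depend on agreement, whatever the dose: "When subjects complete the Treatment Phase and agree to continue receiving the perampanel monotherapy, they could enter the Extension Phase".
- Protocol 9.1.2.1 describes the route to 8 mg: "If subjects experience seizures during the 4 mg Maintenance Period, the investigator will end the 4 mg Maintenance Period", and then judges whether the subject moves to 8 mg titration.
- SAP 8.2, in its definition regardless of dose, says "The subjects who completed the Treatment Phase of the last evaluated dose (ie, 4 or 8 mg) with no seizures will be treated as" seizure-free. It extends this to subjects reduced to 6 mg who complete Maintenance without seizures. Everyone else is non-seizure-free. The definition covers the 26-week Maintenance Period only.

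**The concern.** The period definition was adapted for the second paragraph and the exclusion was not. Within the last-evaluated-dose analysis, two subjects can each complete 26 seizure-free weeks of Maintenance and decline the Extension, yet be handled differently because one was on 4 mg and the other on 8 mg. The list of changes in SAP section 7 gives no reason for a 4 mg-only rule here, and elsewhere in 5.4.2 and 5.4.3 the SAP consistently pairs 4 mg with the last evaluated dose.

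At stake is how one supplementary rate is read. A reader would take it as the 52-week rate with Extension decliners set aside, but only the 4 mg decliners are. Any subjects left in could pull the rate down, never up.

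**Working it through.** **Step 1: does the exclusion reach an 8 mg completer?** Two subjects in the last-evaluated-dose analysis, mITT version:

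| | Subject A | Subject B |
|---|---|---|
| 4 mg Maintenance | completed, no seizure | ended by a seizure |
| 8 mg (or 6 mg) Maintenance | not entered | completed, no seizure |
| 26-week status at last evaluated dose (SAP 8.2) | seizure-free | seizure-free |
| Enters Extension | no | no |
| Completed 4 mg Maintenance? | yes | no |
| Supplementary 52-week analysis | excluded | kept |

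By design a subject reaches 8 mg only after a seizure has ended 4 mg Maintenance, so B cannot meet a condition that requires 4 mg completion. No other provision removes B from the mITT version.

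**Step 2: what status does B receive?** Success needs Maintenance plus 26 weeks of Extension, and B has no Extension. The SAP 8.2 default is non-seizure-free. Excluding A also serves a purpose only if A would otherwise not count as a success. This is an inference: there is no written 52-week rule.

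**Step 3: how large is the effect?** The documents give no figure for this analysis and no number of decliners.

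- Planned mITT size: 72 (Protocol 9.7.2, SAP 4). As a check on that input, 38/72 gives exact 95% limits of 40.65% to 64.67% and power of 0.914 at a true rate of 60%. This agrees with the plan, and the point does not touch it.
- Assumed: 0 or 4 excluded 4 mg decliners, so N = 72 or 72 − 4 = 68.
- Assumed: S = 30 to 40 subjects seizure-free over 52 weeks.
- Assumed: d = 1 or 2 subjects like B.

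The rate as written is S/N. With B also excluded it is S/(N − d). For one decliner the difference is S/(N − 1) − S/N = S/[N(N − 1)].

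| S | N | As written | d = 1 | d = 2 |
|---|---|---|---|---|
| 30 | 72 | 41.7% | 30/71 = 42.3% | 30/70 = 42.9% |
| 36 | 68 | 52.9% | 36/67 = 53.7% | 36/66 = 54.5% |
| 40 | 68 | 58.8% | 40/67 = 59.7% | 40/66 = 60.6% |

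One decliner shifts the rate by between 30/(72 × 71) = 0.6 and 40/(68 × 67) = 0.9 points. Two shift it by about 1.2 to 1.8 points. For scale, the exact 95% interval for 36/68 runs from 40.4% to 65.2%. With d = 0 there is no shift.

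**The case against.** The strongest defence is that a common exclusion may be deliberate. As written, both supplementary rates drop the same people and share a denominator, so their difference is exactly the additional 8 mg successes over that number. Changing one paragraph ends this. With assumed counts of 30 successes at 4 mg and 36 in total, four 4 mg decliners and two 8 mg decliners, the gap is 36/68 − 30/68 = 8.8 points as written and 36/66 − 30/68 = 10.4 points after the change. The extra 1.6 points come only from the denominator. That is a genuine, small cost. It does not settle the matter: the SAP does not state this purpose, and SAP 5.3.3 plans no statistical comparison.

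The number affected may also be very small. Under SAP section 3 and Protocol 9.7.1.6.4, if the primary endpoint is met, subjects still in the 8 mg phase at that analysis count as non-seizure-free and their later data become Extension data. They cannot then be 8 mg completers who decline. The rule does not reach anyone who completed 8 mg before that time. Separately, the population scheduled to complete 52 weeks is undefined and might already omit some decliners, but this does not help the mITT version.

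A reader might infer a loss of 1/72 = 1.4 points per subject. That would be the effect of recoding a failure as a success. The remedy only removes the subject from the denominator, so the shift is smaller.

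**Conclusion.** The inconsistency is real and minor. In the mITT version of the supplementary last-evaluated-dose analysis, 8 mg (or 6 mg) completers who decline the Extension are kept, while 4 mg completers with the same course are removed. The effect is about 0.6 to 0.9 points per decliner, resting on the assumed counts above; it is zero if no 8 mg completer declines, and few subjects may be involved if the rule for achievement of the primary endpoint applies.

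Two stronger readings are tempting. One is that the SAP expressly classes these subjects as failures. It does not: that status follows from the 52-week outcome and the 26-week default, and SAP 8.2 is silent on 52 weeks. The other is that the trial's efficacy conclusion is exposed. It is not: the primary and key secondary 26-week analyses do not use this exclusion, and the secondary 52-week analyses in SAP 5.4.2 exclude no decliners at either dose.

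**What to change.** In the last-evaluated-dose paragraph of SAP 5.4.3, exclude subjects who completed the 26-week Maintenance Period of the last evaluated dose (4 mg, or 8 mg including those reduced to 6 mg) and did not enter the Extension Phase. Leave the 4 mg paragraph unchanged. Show the denominators of both supplementary rates side by side, since they may then differ. If the 4 mg-only rule is intended, state the reason instead. A sentence in SAP 8.2 on the 52-week status of a subject without an Extension would remove the remaining ambiguity.

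The cost is one phrase and one programming condition. Extension entry is already summarised in the disposition tables (SAP 5.2.2), so no new data are needed. The only downside is the loss of a shared denominator.
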